6.3.1. Adverse Events

A treatment-emergent AE (TEAE) is defined as any event occurring during the study not before exposure to study vaccine or any event already present that worsens after exposure to study vaccine. [Note: worsening of a pre-existing condition after vaccination will be reported as a new AE.]

Adverse events will also be evaluated by the investigator for the coexistence of MAAE which is defined as an AE that leads to an unscheduled visit to a healthcare practitioner.

Unsolicited AEs will be coded by PT and SOC using MedDRA and summarized by vaccination group, and stage (up to 28 days after any vaccination for Part 1 and Part 2 separately and overall stage (throughout the study); see Section 6.1 for definitions of vaccination group and stage).

All summary tables (except for the overall summary of AEs) for unsolicited AEs will be presented by SOC and PT for AEs with counts of subjects included. SOC will be displayed in internationally agreed order. PT will be displayed in descending order of frequency of total mRNA-1273.214 group with all dose level combined in Part 1 and mRNA-1273.214 group in Part 2 and then alphabetically within SOC. When summarizing the number and percentage of subjects with an event, subjects with multiple occurrences of the same AE or a continuing AE will be counted once. Subjects will be presented according to the highest severity (the strongest relationship) in the summaries by severity, if subjects reported multiple events under the same SOC and/or PT.

Percentages will be based upon the number of subjects in the Safety Set within each vaccination group for Part 1 and Part 2 separately.

6.3.1.1.Incidence of Adverse Events

An overall summary of unsolicited AEs including the number and percentage of subjects who experience the following will be presented:

- Any unsolicited AEs
- Any serious unsolicited AEs
- Any fatal unsolicited AEs
- Any unsolicited medically-attended AEs
- Any unsolicited AEs leading to discontinuation from study vaccine
- Any unsolicited AEs leading to discontinuation from participation in the study
- Any unsolicited Severe AEs
- Any unsolicited Non-serious AEs
- Any unsolicited Non-serious and Severe AEs
- Any AESI of multisystem inflammatory syndrome in children (MIS-C)
- Any AESI of myocarditis and/or pericarditis
- Any AESI other than MIS-C and myocarditis and/or pericarditis

The table will also include number and percentage of subjects with unsolicited AEs that are treatment-related in each of the above categories.

In addition, separate listings containing individual subject adverse event data for unsolicited AEs, unsolicited AEs leading to discontinuation from study vaccine, unsolicited AEs leading to discontinuation from participation in the study, severe AEs, serious AEs, unsolicited medically-attended AEs, AESI other than MIS-C and myocarditis and/or pericarditis, AESI of MIS-C and AESI of myocarditis and/or pericarditis will be provided separately.

6.3.1.2.AEs by System Organ Class and Preferred Term

The following summary tables of AEs will be provided by SOC and PT using frequency counts and percentages (i.e., number and percentage of subjects with an event):

- All unsolicited AEs
- All unsolicited AEs that are treatment-related
- All serious unsolicited AEs
- All serious unsolicited AEs that are treatment-related
- All unsolicited AEs leading to discontinuation from study vaccine
- All unsolicited AEs leading to discontinuation from participation in the study
- All unsolicited AEs leading to discontinuation from participation in the study that are treatment-related
- All unsolicited Severe AEs
- All unsolicited Severe AEs that are treatment-related
- All unsolicited medically-attended AEs
- All unsolicited medically-attended AEs that are treatment-related
- All AESI of MIS-C
- All AESI of myocarditis and/or pericarditis
- All AESI other than MIS-C and myocarditis and/or pericarditis
- All unsolicited AEs with occurrence in ≥1% of participants in any treatment group based on PT

Additionally, the following summary tables of AEs will be provided by PT using frequency counts and percentages:

- All unsolicited AEs
- All unsolicited AEs, presented by Standardized MedDRA Queries (SMQ) and PT.

6.3.1.3.AEs by System Organ Class, Preferred Term and Severity

The following summary table of AEs will be provided by SOC, PT, and maximum severity (mild < moderate < severe) using frequency counts and percentages:

All unsolicited AEs (Any vs. Related)

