6.3.8. Unblinding

Except in the case of medical necessity, a participant's treatment assignment in Part 2 should not be unblinded without the approval of the Sponsor. If a participant becomes seriously ill during the study, the blind will be broken only if knowledge of the treatment assignment will affect that participant's clinical management. In the event of a medical emergency requiring identification of individual treatment assignment, the investigator will make every attempt to contact the CRO clinical research associate (who must inform the Sponsor medical lead) to explain the need for unblinding within 24 hours of opening the code. The investigator will be responsible for documenting the time, date, reason for unblinding, and the names of the personnel involved. The investigator (or designee) will have access to unblind participants within IRT. All unblindings will be tracked via an audit trail in IRT and documented in the final study report.

If a COVID-19 vaccine (mRNA-1273 or other) is authorized or licensed for infants, parent(s)/LAR(s) of eligible study participants (by virtue of their age) will be offered the opportunity to unblind via a phone call and learn what treatment the participant received, ideally after they have reached at least Day 85 in the study. Participants who have received mRNA-1273.214 will continue in the study and will be followed per protocol. If a participant previously received placebo, then their parent(s)/LAR(s) will be advised to discuss with the participant's primary care physician and follow current CDC recommendations regarding COVID-19 immunization. If a participant who received placebo in the study chooses to receive a nonstudy COVID-19 vaccine, they will be withdrawn from the study.

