- b) study day on or after the date of the first injection but before the second injection (if applicable) will be calculated as: date of assessment/event date of the first injection + 1;
- c) study day on or after the date of the second injection will be calculated as: date of assessment/event date of the second injection + 1; if study day is on the same day as the second injection, date and time will be compared with the second injection date and time. If time is prior to the time of second injection, then study day is calculated as: date of assessment/event date of the first injection + 1; If it is after the time of second injection or the time is missing or not available then study day is calculated as: date of assessment/event date of the second injection + 1.

For calculation regarding antibody levels/concentrations, antibody values reported as below LLOQ will be replaced by 0.5 × LLOQ. Values that are greater than the upper limit of quantification (ULOQ) will be converted to the ULOQ if actual values are not available, and actual values will be used if available. Missing results will not be imputed.

The following analysis periods or stages for safety analyses will be used in this study:

- Up to 28 days after any vaccination: this stage starts at the day of each vaccination and continue through the earliest date of (the day of each vaccination and 27 subsequent days, next vaccination [if applicable]). This analysis period will be used as the primary analysis period for safety analyses including unsolicited AE, except for solicited AR, unless specified otherwise.
- Overall period (throughout the study): this analysis period starts at the first injection on Day 1 and continues through the earliest date of (study completion, discontinuation from the study, or death).

Unscheduled visits: Unscheduled visit measurements will be included in analysis as follows:

- In scheduled visit windows per specified visit windowing rules.
- In the derivation of baseline/last on-treatment measurements.
- In the derivation of maximum/minimum on-treatment values and maximum/minimum change from baseline values for safety analyses.
- In individual subject data listings as appropriate.

Visit windowing rules: The analysis visit windows for protocol-defined visits are provided in Appendix B.

Incomplete/missing data:

- Imputation rules for missing prior/concomitant medications, non-study vaccinations and procedures are provided in Appendix C.

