- Imputation rules for missing AE dates are provided in Appendix D.
- For laboratory assessments, if majority of results are indefinite, imputation of these values will be considered. If the laboratory results are reported as below the LLOQ (e.g., <0.1), the numeric values will be imputed by 0.5 × LLOQ in the summary. If the laboratory results are reported as greater than the ULOQ (e.g., >3000), the numeric values will be imputed by ULOQ in the summary.
- Other incomplete/missing data will not be imputed, unless specified otherwise.

Treatment groups:

The following vaccination groups will be used for summary purposes:

- Part 1, Open-Label Phase:
 - o mRNA-1273.214 5 μg
 - o mRNA-1273.214 10 μg
 - o mRNA-1273.214 Total
- Part 2, Blinded Phase:

Treatment in Part 2 will be the selected dose level from Part 1 or Placebo

- o mRNA-1273.214 5 μg, or
- o mRNA-1273.214 10 μg

And

o Placebo

Subjects who received at least one dose of mRNA-1273.214 in Part 2 will be included in the mRNA-1273.214 selected dose level group (as actual treatment) in Part 2 in the safety and immunogenicity analyses.

External comparator:

• Comparator: mRNA-1273 100 μg primary series (from study P301 in young adult participants (18-25 years) who received 2 doses of mRNA-1273 primary series)

Summary by study part:

Separate shells will be provided for Part 1 and Part 2 of the study. All analyses and data summaries/displays will be provided by vaccination group.

Analysis Periods

The following analysis periods and treatment groups will be used for efficacy or immunogenicity analyses for Part 2, the blinded phase, unless specified otherwise:

Part 2 Group	Description	Part 2 Blinded Phase Analysis Period for Efficacy or Immunogenicity
mRNA-1273.214	Participants randomized to mRNA-1273.214 in the Blinded Phase	From randomization to earliest date of unblinding (inclusive), study

Diagram	Participants randomized to	discontinuation, study completion,
Placebo	Placebo in the Blinded Phase	death, and data cutoff date

The following analysis period and treatment groups will be used for safety analysis for Part 2, the blinded phase, unless specified otherwise:

Part 2 Group	Description	Part 2 Blinded Phase Analysis Period for Safety
mRNA-1273.214	Participants received at least one dose of mRNA-1273.214 in the Blinded Phase	From the date of first injection to the earliest date of unblinding (inclusive),

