6.7. Data Safety Monitoring Board

Safety oversight will be under the direction of a DSMB composed of external, independent consultants with relevant expertise. Members of the DSMB will be independent from study conduct and free of conflict of interest. The DSMB will operate under the rules of an approved charter that will be written and reviewed at the organizational meeting of the DSMB. Details regarding the DSMB composition, responsibilities, procedures, and frequency of data review will be defined in its charter. Statistical analysis outputs for the DSMB review will also be specified in the charter.

7. Changes from Planned Analyses in Protocol

On 18Sep2023, the study initiated an enrollment pause in direct response to emergency use authorization of an updated COVID-19 vaccine in children 6 months of age and older in the United States. Prior to the enrollment pause, 18 participants were enrolled in Part 1 Arm 2. As a result, the Part 1 Arm 2 interim analysis will be conducted after 18 participants have completed 28 days after last dose of mRNA-1273.214 rather than after the total planned enrollment in this arm (50 participants). This change does not impact the primary and/or key secondary objectives/hypotheses or the related statistical methods.

8. References

Department of Health and Human Services (DHHS), Food and Drug Administration, Center for Biologics Evaluation and Research (US). Guidance for industry: Toxicity grading scale for healthy adult and adolescent volunteers enrolled in preventative vaccine clinical trials. September2007[cited2019 Apr 10][10 screens]. Available from: https://www.fda.gov/downloads/BiologicsBloodVaccines/GuidanceComplianceRegulatory Information/Guidances/Vaccines/ucm091977.pdf.

9. List of Appendices

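### SAP 6.1 gives two end points for Part 2 safety follow-up; if the one that ignores unblinding governs, crude whole-study MAAE, SAE and AESI percentages are biased against the vaccine

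*SAP*

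**What the plan says.** MAAEs, SAEs and AESIs over the entire study are primary safety endpoints (SAP 3.1). SAP 6.3.1 summarises unsolicited events by vaccination group for a 28-day stage and for an "overall stage (throughout the study" stage, and refers back to SAP 6.1 for the definitions. The denominator is a head count: "Percentages will be based upon the number of subjects in the Safety Set within each vaccination group for Part 1 and Part 2 separately".

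SAP 6.1 then defines the end of safety follow-up twice.

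- In the list of safety analysis periods: "Overall period (throughout the study): this analysis period starts at the first injection on Day 1", and it "continues through the earliest date of (study completion, discontinuation from the study, or death". Unblinding is not among the end points.
- In the Part 2 group table: "The following analysis period and treatment groups will be used for safety analysis for Part 2, the blinded phase, unless specified otherwise". That period runs "From the date of first injection to the earliest date of unblinding (inclusive", or to discontinuation, completion, death or data cutoff if earlier. It applies to both arms.

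Protocol 6.3.8, repeated in SAP 4.5, says what follows authorisation of a COVID-19 vaccine for infants. Parents of age-eligible participants in either arm are offered unblinding, ideally from Day 85. Infants found to have received mRNA-1273.214 stay in follow-up. For the others: "If a participant who received placebo in the study chooses to receive a nonstudy COVID-19 vaccine, they will be withdrawn from the study".

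SAP Section 7 records an "emergency use authorization of an updated COVID-19 vaccine in children 6 months of age and older".

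**The concern.** Part 2 has a placebo arm so that safety can be assessed against a control (Protocol 4.2). A crude percentage is a fair between-arm summary only if the arms are followed for similar lengths of time. Here the withdrawal rule shortens follow-up in one arm only. An infant withdrawn at about 3 months cannot contribute an MAAE in months 4 to 14 but stays in the denominator.

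The trigger is realistic. An infant aged 12 weeks at Day 1 is 12 + 14 = 26 weeks old at Day 99, so every participant reaches about 6 months of age early in follow-up to Day 422. The plan uses person-time for COVID-19 and infection incidence (SAP 6.5.2) but not for adverse events. If the overall period governs, an apparent excess in the vaccine arm could come from follow-up alone.

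**Working it through.** **1. The plan's own safety figure.** The documents state no expected whole-study MAAE, SAE or AESI rate. The nearest figure is the claim of at least 90% probability of seeing at least one participant with an AE of 1% true rate among about 300 vaccinated infants (SAP 4.3). 1 − 0.99^300 = 95.1%, so the claim holds. It concerns one arm and says nothing about the comparison.

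**2. Inputs.** From the documents: 300 infants per arm, follow-up of about 14 months (Day 422), and withdrawal in placebo only. Assumed, because the documents give none of them: event risk R over full follow-up, share u of placebo infants withdrawn, and time f of withdrawal. The hazard is taken as constant and equal in both arms, that is, no vaccine effect.

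**3. Formula if the overall period governs.** Vaccine arm: R. Placebo arm: (1 − u)R + u[1 − (1 − R)^(f/14)], with f in months.

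**4. Results for R = 20%, f = 3 months.** 1 − 0.80^(3/14) = 4.7%.

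- u = 25%: 0.75 × 20.0 + 0.25 × 4.7 = 16.2%. 20.0% versus 16.2%, ratio 1.24.
- u = 50%: 0.50 × 20.0 + 0.50 × 4.7 = 12.3%. 20.0% versus 12.3%, ratio 1.62.

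Later withdrawal shrinks the effect. With u = 25%, withdrawal at 6, 8 or 10 months gives infant-level risks of 9.1%, 12.0% and 14.7%, and arm-level ratios of about 1.16, 1.11 and 1.07.

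**5. Other risks (same formula in days, f/14 replaced by 85/422).**

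- Common events, u = 25%: R = 60% gives 60.0% versus 49.2% (ratio 1.22); R = 40% gives 40.0% versus 32.4% (ratio 1.23). By normal approximation with 300 per arm, a Wald 95% CI for the difference would lie wholly above zero with probability 76% and 49% respectively, against a nominal 2.5%.
- Rare events: R = 1% with u = 25% gives 1.00% versus 0.80%, a gap of 0.2 points. R = 3% with u = 50% gives 3.00% versus 1.81%, a gap of 1.2 points.

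**6. If the blinded-phase period governs.** Both arms stop at unblinding by the same rule, and parents choose before knowing the assignment. If the same share unblinds at the same time in each arm, the R = 20%, u = 25%, 3-month case becomes 16.2% versus 16.2%. The expected difference is zero for any R, u and f, even with crude percentages.

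**7. Person-time.** Under a constant hazard, events divided by person-time to first event gives a rate ratio of 1.00 in every scenario above. If event rates change with age, person-time alone does not fully correct, because the lost placebo time is all late. Ending both arms at unblinding does not depend on that assumption.

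**The case against.** The strongest reply is that SAP 6.1 already contains the remedy. The blinded-phase safety period is the stated default for Part 2 and ends both arms at unblinding. A reader might infer from the withdrawal rule that a harmless vaccine will look harmful under the plan as written. The documents do not support that unconditionally, because under the default period the expected excess disappears.

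This reply does not settle the matter. The default yields where something else is specified, and SAP 6.3.1 does specify an overall stage and points to SAP 6.1, where that stage runs past unblinding. The endpoints are also worded as covering the whole study, which a cut at unblinding would not. The text leans towards the overall period for these tables but never says so.

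A reader might also set a fully followed vaccine infant (20.0%) against a placebo infant withdrawn at 3 months (4.7%) and quote a ratio of 4.3. The tables report arms, so that ratio would need every placebo infant to leave at 3 months. Nothing in the documents suggests this.

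Other safeguards carry some weight. The 28-day window is the primary safety period and largely precedes the Day 85 unblinding offer. Study duration is summarised (SAP 6.2.5), so unequal follow-up would be visible. No between-arm test of adverse events is planned, and Protocol Table 9 gives confidence intervals only for solicited reactions. But safety is judged by clinical review of these group summaries (SAP 6.3), and a reviewer reads the two percentages side by side whether or not a test accompanies them.

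**Conclusion.** The SAP gives two incompatible end points for a primary safety analysis in Part 2 and does not say which governs the whole-study MAAE, SAE and AESI tables. If the overall period governs, the crude percentages carry an expected bias against the vaccine. If the blinded-phase period governs, the expected difference under no effect is about zero. A small residual could remain if parents guess the arm from reactogenicity before deciding to unblind.

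The direction under the overall period is clear. The size is only moderately certain, because it depends on uptake, timing and event risk, none of which the documents give. At 25% to 50% withdrawn and 20% risk, the arm-level ratio is about 1.24 to 1.62 for withdrawal at 3 months, and less for later withdrawal. For SAEs and AESIs at 1% to 3% risk, the distortion is about 0.2 to 1.2 points.

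The point concerns Part 2 only, since Part 1 has no placebo arm. The enrolment pause in SAP Section 7 was recorded during Part 1 Arm 2. It shows that the authorisation trigger is real, but says nothing about uptake among placebo families. The SAP should be corrected before any Part 2 safety analysis.

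**What to change.** In SAP 6.3.1:

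1. State that the Part 2 between-arm whole-study tables of MAAEs, SAEs, AESIs and AEs leading to discontinuation use the blinded-phase safety period of SAP 6.1, with both arms ending at unblinding if it comes first.
2. Add exposure-adjusted incidence to those tables: participants with an event per 100 person-years from first injection, in the Safety Set as treated, with an exact 95% CI.
3. Show events after unblinding in a separate table, so that whole-study data in vaccinated infants are still reported but not set against a depleted placebo arm.
4. Keep crude percentages for the 28-day window.

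The cost is extra table columns, one additional display and a new person-time derivation. The person-time in SAP 6.5.2 cannot be reused as it stands: it runs from randomisation to infection events in the efficacy sets, by randomised group. The dates needed are already used for study duration in SAP 6.2.5. No visit, procedure or withdrawal rule changes.

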Reaction	Grade 0	Grade 1	Grade 2	Grade 3	Grade 4 ¹
Groin or underarm swelling or tenderness ipsilateral to the side of injection	None	Some swelling or tenderness but no interference with normal daily activities	Swelling or tenderness that interferes with normal daily activities	Swelling or tenderness that prevents normal daily activities	Emergency room visit ² or hospitalization
Systemic Reaction					
Fever	< 38.0°C	38.0-38.4°C 100.4-101.1°F	38.5-39.5°C 101.2-103.1°F	39.6-40.0°C 103.2-104.0°F	> 40.0°C > 104.0°F
Irritability/crying	None	Lasting < 1 hour or easily consolable	Lasting 1 to 3 hours or requiring increased attention	Lasting > 3 hours or inconsolable	Requires emergency room visit ² or hospitalization
Sleepiness	None	Sleepier than usual or less interested in surroundings	Not interested in surroundings or sleeps through meals	Sleeps most of the time, hard to arouse	Inability to arouse
Loss of appetite	None	Eating less than normal for 1-2 feeds/meals	Missed 1-2 feeds/ meals completely	Missed > 2 feeds/meals completely or refuses most feeds/meals	Requires emergency room visit ² or hospitalization

Abbreviations: AE = adverse event; eCRF = electronic case report form.

Note: Events listed above but starting > 7 days post-study injection will be recorded on the AE page of the eCRF. Causality for each event will be determined per assessment by the investigator.

Source: Guidance for Industry: Toxicity Grading Scale for Healthy Adult and Adolescent Volunteers Enrolled in Preventative Vaccine Clinical Trials (DHHS 2007).

Any solicited AR that meets any of the following criteria must be entered into the participant's source document and must also be recorded by the study site staff on the solicited AR page of the participant's eCRF:

- Solicited local or systemic AR that results in a visit to an HCP (otherwise meets the definition of an MAAE)
- Solicited local or systemic AR leading to the participant withdrawing from the study or the participant being withdrawn from the study by the investigator (AE leading to withdrawal)
- Solicited local or systemic AR lasting beyond 7 days after injection

^{1.} Grading for Grade 4 events per investigator assessment (with exception of fever).

^{2.} Emergency room visit includes urgent care visit.

Protocol: mRNA-1273-P206, Original

• Solicited local or systemic AR that leads to participant withdrawal from IP

• Solicited local or systemic AR that otherwise meets the definition of an SAE

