9.5.2. Safety Analyses

All safety analyses will be based on the Safety Set, except summaries of solicited ARs, which will be based on the Solicited Safety Set. All safety analyses will be provided by vaccination group (dose levels of mRNA-1273.214 and placebo).

Safety and reactogenicity will be assessed by clinical review of all relevant parameters including solicited ARs (local and systemic events), unsolicited AEs, SAEs, MAAEs, AESIs, and AEs leading to discontinuation from IP and/or study participation.

The number and percentage of participants with any solicited local AR, with any solicited systemic AR, and with any solicited AR during the 7-day follow-up period after each injection by toxicity grade will be provided. A 2-sided 95% exact CI using the Clopper-Pearson method will also be provided for the percentage of participants with any solicited AR.

The number and percentage of participants with unsolicited AEs, SAEs, MAAEs, severe AEs, and AEs leading to discontinuation from IP or withdrawal from the study will be summarized. Unsolicited AEs will be presented by MedDRA preferred term and system organ class.

Solicited AR events (starting within 7 days after any injection) that are serious or lasting beyond Day 7 after any injection will also be reported as unsolicited AEs.

The number of events of solicited ARs, unsolicited AEs/SAEs, MAAEs, severe AEs, and AEs leading to discontinuation from IP or withdrawal from the study will be reported in summary tables accordingly.

Protocol: mRNA-1273-P206, Original

For all other safety parameters, descriptive summary statistics will be provided, and Table 9 summarizes the analysis strategy for safety endpoints. Further details will be described in the SAP.

Table 9: Analysis Strategy for Safety Parameters

Safety Endpoint	Number and Percentage of Participants, Number of Events	95% CI
Any solicited AR (overall and by local, systemic)	X	X
Any unsolicited AE	X	-
Any SAE	X	_
Any unsolicited MAAE	X	_
Any unsolicited treatment-related AE	X	_
Any treatment-related SAE	X	_
Discontinuation due to AE	X	_
Any severe AE	X	_
Any treatment-related severe AE	X	_
Any AESI	X	-

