3.1. Primary Endpoints

The primary safety objective for Part 1 and Part 2 will be evaluated by the following safety endpoints:

- Solicited local and systemic adverse reactions (ARs) through 7 days after each injection
- Unsolicited adverse events (AEs) through 28 days after each injection
- Medically attended AEs (MAAEs) throughout the entire study period
- Serious AEs (SAEs) throughout the entire study period
- AEs of special interest (AESIs) throughout the entire study period
- AEs leading to discontinuation from study participation postdose throughout the entire study period

The primary immunogenicity objective to infer effectiveness of the mRNA-1273.214 vaccine for Part 2 will be evaluated by:

- Co-primary Endpoint: geometric mean (GM) value of antibodies (Ab) against SARS-CoV-2 VOC (Omicron) at 28 days after the second dose of mRNA-1273.214 compared with that of the adult participants at Day 57 (28 days after the second dose) in Study mRNA-1273-P301 dosed with mRNA-1273 (100 μg, 2 doses 28 days apart) primary series
- Co-primary Endpoint: seroresponse rate (SRR) against SARS-CoV-2 VOC (Omicron) at 28 days after the second dose of mRNA-1273.214 compared with that of the adult participants at Day 57 (28 days after the second dose) in Study

mRNA-1273-P301 dosed with mRNA-1273 (100 μg , 2 doses 28 days apart) primary series

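### The SAP's medically attended AE and AE-discontinuation tables count only unsolicited AEs, so short-lived, non-serious solicited reactions that prompt an HCP visit or withdrawal drop out of two primary safety endpoints

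*SAP*

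**What the plan says.** SAP 3.1 gives six primary safety endpoints for both parts. One is expressly solicited reactions and one is expressly unsolicited AEs. MAAEs, SAEs, AESIs and AEs leading to study discontinuation carry neither label; the SAE item, for example, reads "Serious AEs (SAEs) throughout the entire study period".

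The tables are narrower. The overall summary in SAP 6.3.1.1 has the rows "Any serious unsolicited AEs", "Any unsolicited medically-attended AEs" and "Any unsolicited AEs leading to discontinuation from participation in the study", plus a similarly limited row for discontinuation of study vaccine. SAP 6.3.1.2 follows suit, for example with "All unsolicited medically-attended AEs". The listings for MAAEs and discontinuations are also limited to unsolicited events; the serious AE listing is not.

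Protocol 8.11.3 names solicited reactions that need extra recording: those leading to an HCP visit, to withdrawal from the study or from investigational product, or lasting beyond 7 days, and any "Solicited local or systemic AR that otherwise meets the definition of an SAE". Each of these "must also be recorded by the study site staff on the solicited AR page of the participant's eCRF".

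Protocol 9.5.2, and the synopsis, add a carry-over rule: solicited reactions starting within 7 days of injection "that are serious or lasting beyond Day 7 after any injection will also be reported as unsolicited AEs".

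**The concern.** Three primary endpoints are stated without restriction but tabulated with one. A reader of the MAAE table would take it as the count of infants whose vaccination was followed by an event needing medical attention. If early reactions are left out, that count omits the events closest in time to the injection, which SAP 6.3.2 treats as causally related to it. The same applies to the table of AEs leading to discontinuation.

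The point matters in this age group because the expected reactions are short. Protocol 2.2 reports that in children aged 6 months to under 6 years reactogenicity mostly lasted 2 to 3 days, with a median fever duration of 1 day. A rule that rescues only reactions lasting beyond Day 7 would miss most of these.

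**Working it through.** There is no figure in the plan to reproduce. The check is to follow a solicited reaction through the definitions and see which table it reaches.

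1. Is it an unsolicited AE? Protocol 8.11.1 counts a listed reaction as unsolicited only if it starts outside the day of injection and the 6 days after it. A reaction starting inside that window is not.
2. Where is it recorded? On the solicited reaction page (Protocol 8.11.3), including when it meets the MAAE definition or causes withdrawal.
3. Does the carry-over rule bring it back? Protocol 9.5.2 has two triggers: serious, or lasting beyond Day 7. Medical attendance and withdrawal are not triggers.
4. Does another safety output show it? The solicited reaction outputs in SAP 6.3.2 give grade, day, onset, duration and persistence. None gives medical attendance or discontinuation.

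| Solicited reaction starting within the window | Unsolicited under 8.11.1 | Carried over under 9.5.2 | Where it appears in SAP 6.3.1 |
|---|---|---|---|
| Serious, such as an inpatient admission | No | Yes | Serious AE row through the carry-over rule; also the serious AE listing |
| Non-serious, lasting beyond Day 7, with HCP visit or withdrawal | No | Yes | MAAE or discontinuation row through the carry-over rule |
| Non-serious, over by Day 7, with HCP visit | No | No | No MAAE row or listing |
| Non-serious, over by Day 7, with withdrawal | No | No | No discontinuation row or listing |

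The last two lines are the gap. It touches two endpoints: MAAEs and AEs leading to study discontinuation.

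Some of these events show through the severity grades, but only in part. In Protocol Table 7, Grade 4 is defined by an emergency room visit (urgent care included) or hospitalisation for 4 of the 8 reactions: pain or tenderness, groin or underarm swelling, irritability, and loss of appetite. An urgent care visit without admission does not meet the hospitalisation criterion for an SAE in Protocol 8.11.2, so it may be an MAAE with no MAAE row. Grade 4 also mixes urgent care, emergency room and hospital, leaves out ordinary clinic visits, and is set by temperature alone for fever.

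The documents give no rate of medically attended or discontinuing solicited reactions, so the shortfall cannot be estimated. The weight of one omitted infant can be:

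- Part 1 Arm 2 as enrolled (SAP Section 7): 1/18 = 5.6%
- Part 1 Arm 1 as planned: 1/50 = 2.0%
- One Part 2 arm as planned: 1/300 = 0.3%

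**The case against.** The strongest reply is that the protocol plans it this way. The MAAE row of Protocol Table 9 carries the unsolicited limit, and Protocol 8.11.4 has investigators look for MAAEs among unsolicited AEs. On MAAEs, then, the SAP follows the protocol. That is correct, but it shows that both documents share the mismatch with the stated endpoint; it does not remove it. On discontinuation the reply is weaker, because the Table 9 row has no such limit and the SAP narrows it without listing a change in Section 7.

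A second reply is that withdrawals are counted elsewhere. SAP 6.2.1 tabulates study discontinuation by vaccination group and reason, and Protocol 7.3 includes AE and SAE among the reasons. This stands: such an infant is not invisible. But the disposition table gives no event term and is not the safety endpoint. In Part 2 it uses infants as randomised, whereas the Safety Set is as treated. It could show more AE withdrawals than the safety table with nothing to explain the difference.

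A third reply concerns serious events, and it succeeds. A reader might infer from the row labels that an infant admitted with fever in the first week is in no SAE table, so that three endpoints are incomplete. The documents do not support that. Admission makes the event serious (Protocol 8.11.2), and the 9.5.2 rule then places it among the unsolicited AEs. SAP Section 1 lets the SAP prevail where methods differ, but silence is not a difference, and SAP Section 7 declares no change to the rule. Nor would a febrile seizure be lost: seizure is not a Table 7 reaction, and it is an AESI in Protocol Appendix 2.

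**Conclusion.** The point holds for two primary safety endpoints, MAAEs and AEs leading to study discontinuation, in both parts of the study. The reactions affected are solicited, non-serious and resolved by Day 7. Those leading to withdrawal still appear by reason in the disposition table, but not by term or as a safety endpoint.

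For SAEs the defect is one of clarity. The tables are labelled as serious unsolicited AEs, the listing as serious AEs, and the rule that reconciles them is in the protocol only.

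This rests on two readings: that the 9.5.2 rule still applies although the SAP does not repeat it, and that sites follow 8.11.3 and do not also enter these reactions on the AE page.

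A reader might also infer that the omission makes the vaccine look safer than placebo. Protocol 2.3.2 reports more solicited reactions with vaccine than placebo in both earlier studies, so that direction is plausible for Part 2. It is not established: the rule that solicited reactions are treated as related covers placebo too, and no rates are given for the affected events. Part 1 has no placebo arm.

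**What to change.** In SAP 6.3.1.1 and 6.3.1.2, define the MAAE and discontinuation rows, tables and listings as all AEs meeting the criterion, solicited and unsolicited, drawn from both the AE and the reactogenicity eCRF pages. Keep the unsolicited-only count as a sub-line, so that the current display is not lost. Align the MAAE row of Protocol Table 9.

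In SAP 6.3.1, restate the Protocol 9.5.2 rule that serious or prolonged solicited reactions are also reported as unsolicited AEs, so that the SAE tables and the listing agree.

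The cost is SAP wording, one protocol table row and a few extra output rows. Protocol 8.11.3 already requires these reactions on the eCRF; the sponsor should confirm that the page records why each was entered (HCP visit, or withdrawal from study or product). The displayed MAAE and discontinuation rates will be slightly higher.
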